**CBT-I Intervention Protocol Summary.** The CBT-I intervention will be delivered individually and in person by one of the therapists, over six one-hour weekly sessions. In circumstances where in-person visits prevent participation, the CBT-I intervention can be delivered via telephone. The CBT-I protocol is summarized below:

**Session 1: Sleep Education and Introductions to CBT-I and Sleep Diaries.** Participants will receive an overview of CBT-I treatment concepts and approach, in addition to education about sleep regulation processes and the cognitive and behavioral processes involved in the development of insomnia. At the end of the session, they will be instructed in establishing realistic treatment goals and the process for keeping weekly sleep diaries.

**Session 2: Introduction to Sleep Restriction Therapy and Stimulus Control.** The therapist will introduce Stimulus Control and Sleep Restriction Therapy guidelines and rationale. Sleep Restriction Therapy (SRT) is designed to strengthen the homeostatic sleep drive by restricting time in bed to actual sleep time as determined by sleep diary. The sleep “prescription”, or allowable sleep window, is gradually increased over the course of treatment to extend sleep duration. Stimulus Control is a set of instructions designed to strengthen the association between the bed/bedroom and sleep, and to establish a consistent sleep–wake schedule. Participants will receive education and intervention based on treatment targets identified in Session 1 in addition to the sleep pattern information gleaned from the sleep diary review. Sleep hygiene education will be provided for topics that are relevant to the participant (e.g., the effects of alcohol on sleep). An initial “sleep prescription” will be established and participants will be asked to follow this sleep schedule during the upcoming week. Cognitive therapy will be used, as needed, to address dysfunctional beliefs about sleep and to enhance adherence.

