**Actigraphy Sleep Assessments.** Sleep and daily physical activity will be recorded using an accelerometer (Actigraph GT9X Link, Actigraph, Pensacola, Florida), unobtrusively worn on the wrist of the non-dominant arm. The Actigraph GT9X monitor is a small, lightweight device that utilizes a 3-axis MEMS accelerometer, with motion sampled at a frequency of 30-100 Hz, and has been utilized and validated in both healthy and patient populations. Participants will wear the Actigraph 24 hours/day for 7 consecutive days, at baseline, upon completion of the 6-week run-in period, upon completion of the CBT-I intervention, and at 6-month followup. The actigraphy data will be processed using ActiLife and ActiLife+Sleep software (Actigraph, Pensacola, Florida), which was developed in collaboration with the US and international sleep and activity research community; scoring of actigraphy data will proceed in accordance with the guidelines of the Society of Behavioral Sleep Medicine. Recorded sleep log times, confirmed by an event marker, will be used to establish “lights out” and “out of bed” times. ActiLife+Sleep software will be used to derive our primary outcome measure of sleep quality, sleep efficiency (SE). Other sleep parameters of interest will be Time in Bed (TIB), total sleep time (TST), wake after sleep onset (WASO), and sleep fragmentation index (SFI). Sleep duration will be defined as TST (calculated by subtracting all periods of wakefulness from the time spent in bed). WASO is calculated by summing wakefulness periods after initial sleep onset and before final awakening. Sleep efficiency is defined as the ratio of total sleep time divided by TIB  $((TST/TIB)*100)$ . Sleep fragmentation is defined as the sum of percent mobile and percent immobile bouts less than 1-minute duration to the number of immobile bouts for a given interval. Actigraphy also provides reliable measurements of daily life physical activity and has been extensively validated against self-report, observational measures, and oxygen consumption estimates of physical activity. Therefore, the ActiLife software will also be utilized to derive daily cumulative step count and daily energy expenditure (kcal/d). All physical activity and sleep parameters derived using actigraphy will be based on the 8-consecutive-days monitoring protocol and represented as average daily activity/sleep values at each assessment phase (baseline, upon completion of the 6-week run-in period, upon completion of the CBT-I intervention, and at 6-month follow-up).

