#### C.5. ASSESSMENT OF MECHANISMS OF CARDIOVASCULAR RISK

The following laboratory-based and ambulatory assessments will be completed at baseline and repeated following the 6-week run-in control period, following the 6-week CBT-I intervention, and at 6-month follow up. Assessors will be blinded to the study phase at which data are collected.

Office BP Assessment. Automated office BP (AOBP) will be obtained using the Omron HEM-907

Professional Intellisense BP Monitor. The office BP assessment protocol is described under “Office BP Screening Assessment” described earlier in this application.

24-hour Ambulatory Blood Pressure (ABP) Monitoring. We will use the Oscar 2 ABP monitor (Suntech Medical Inc., Raleigh, NC), which has been validated previously according to US and International standards. Study participants will be instrumented with the ABP monitor between 6:00-10:00 am on a typical weekday (Mon-Fri), and the monitor will be programmed to take BP measurements every 20 minutes throughout the waking hours and every 30 minutes during the nighttime sleep period. We have used this procedure with excellent participant acceptability and compliance in numerous previous studies. A successful 24-hour study will require at least 80% of the total readings to be valid, with no more than two consecutive hours lacking a valid reading, and at least one valid measurement per hour during the nighttime sleep period. Unsuccessful ABP studies will be repeated. Because a single 24-hour ABPM record has been shown to be of greater prognostic value than multiple clinic BP readings, it has become an accepted gold standard for evaluating intervention effects on BP. In addition to mean 24-hour ABP, mean waking and mean nighttime BP will be computed, with the nighttime sleep period defined by self-reported sleep logs, in accordance with the Society for Behavioral Sleep Medicine (SBSM) guidelines. Nighttime BP dipping will be defined as the percentage of the decline in nighttime SBP ( $((\text{mean daytime SBP} - \text{mean nighttime SBP}) / \text{mean daytime SBP}) \times 100$ ); SBP dipping defined in this way is a continuous variable that will be a primary outcome measure of sleep-related CVD risk mechanisms in

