the proposed study. In addition, for descriptive purposes, a SBP dip  $\geq 10\%$  will be classified as normal “dipper”, while  $<10\%$  will be classified as “non-dipper”, with secondary analyses evaluating intervention effects on dipping status. As noted earlier in this application, the causes and consequences of blunted nighttime BP dipping has been a focus of our prior research. Importantly, our recent work shows that ABPM does not disturb sleep, and a single successful 24-hour ABP study provides adequate representation of the diurnal ABP profile in patients with hypertension. 24-hour ABP assessments will be obtained.

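### Sleep efficiency and SBP dipping share a sleep-log window that CBT-I deliberately changes, and the primary model has no term for that change

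*Combined protocol and SAP*

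**What the plan says.** **Exposure.** In C.4, the limits of the time in bed come from the log: "Recorded sleep log times, confirmed by an event marker, will be used to establish" lights-out and out-of-bed times. Then "Sleep efficiency is defined as the ratio of total sleep time divided by TIB", so the window length is the denominator. Values are averaged over the monitoring period: "Participants will wear the Actigraph 24 hours/day for 7 consecutive days" (the same paragraph later says eight days).

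**Outcome.** In C.5, waking and nighttime BP are computed "with the nighttime sleep period defined by self-reported sleep logs". Dipping is the percentage fall from the daytime to the nighttime SBP mean and is a primary outcome. It rests on one record per assessment, on the ground that "a single successful 24-hour ABP study provides adequate representation of the diurnal ABP profile".

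**Intervention.** Session 2 in C.3, repeated under Study Interventions, describes sleep restriction as "restricting time in bed to actual sleep time as determined by sleep diary". The next sentence says that the allowed window is widened step by step during treatment.

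**Model.** The Aim 1 analysis plan regresses post-treatment dipping on improvement in sleep quality. It adjusts for age, gender, race, baseline sleep efficiency, baseline 24-hour BP and pre-treatment dipping. No covariate describes change in time in bed or in the ABP night. Nighttime mean BP and 24-hour mean BP are analysed in parallel.

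**The concern.** Shortening time in bed at constant total sleep time raises sleep efficiency by definition. It also moves readings taken awake in bed from the night mean to the day mean. If SBP at those times is close to the waking level, the night mean falls and the computed dip deepens although no reading has changed. If it is close to the sleep level, the day mean falls instead and the computed dip becomes shallower. Both shifts depend on how much each participant's window changed, so they can create, inflate or mask the association that Aim 1 tests.

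The study is mechanistic and has no randomised comparator, so Aim 1 rests on this association. Dipping status at the 10% threshold, a secondary analysis, is exposed in the same way.

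**Working it through.** **1. The plan's own figures.** These reproduce.
- Correlation: N = 150 × 0.85 = 127.5, taken as 127. Power for r = 0.25 is Φ(atanh(0.25) × √124 − 1.96) = 0.81, against the stated 80%.
- Thirds: 2 × ((1.96 + 1.04)/0.6)² = 50 per group. A difference of 2.2 points at effect size 0.6 implies a dipping SD of 2.2/0.6 = 3.67.

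**2. Within-person shift.** Assumptions, none of them in the documents: waking SBP 140; sleep SBP 12% lower (123.2); total sleep time 6.4 h; time in bed 8.5 h before and 7.0 h after; the ABP night equals the full time in bed; every clock-time BP unchanged. Let b be awake-in-bed SBP.
- Night mean for a window of T hours = (6.4 × 123.2 + (T − 6.4) × b)/T
- Day mean = (15.5 × 140 + (8.5 − T) × b)/(24 − T)
- Dip = 100 × (day − night)/day

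Sleep efficiency goes from 6.4/8.5 = 75% to 6.4/7.0 = 91%. For b = 140, the night mean falls from 127.35 to 124.64, the day mean stays at 140, and the dip goes from 9.04% to 10.97%, crossing the 10% threshold.

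| Awake-in-bed SBP below waking | Dip at 8.5 h | Dip at 7.0 h | Shift (points) |
|---|---|---|---|
| 0% | 9.04 | 10.97 | +1.94 |
| 5% | 10.27 | 11.01 | +0.74 |
| 8% | 11.01 | 11.03 | +0.02 |
| 10% | 11.51 | 11.04 | −0.46 |
| 12% (sleep level) | 12.00 | 11.06 | −0.94 |

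In every row the 24-hour mean is unchanged.

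**3. Between-thirds difference.** The plan's 2.2 points is a contrast between the best and worst thirds of sleep-efficiency change, and everyone receives CBT-I, so only differences in the window cut count. Compare a third cutting 1.5 h (8.5 to 7.0) with a third cutting 0.5 h (8.5 to 8.0).

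| Awake-in-bed SBP below waking | Shift, 1.5 h cut | Shift, 0.5 h cut | Difference |
|---|---|---|---|
| 0% | +1.94 | +0.56 | +1.37 |
| 5% | +0.74 | +0.19 | +0.55 |
| 8% | +0.02 | −0.03 | +0.05 |
| 12% | −0.94 | −0.33 | −0.61 |

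At the favourable end this is 1.37/2.2 = 62% of the planned contrast; at 8% below waking it is 2%.

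**4. Simulation with no true effect.** Post-treatment dipping was regressed on change in sleep efficiency, baseline sleep efficiency and pre-treatment dipping, with N = 127, dipping SD 3.67 and 2,000 runs per scenario. Assumed: sleep SBP 122 against 140 by day, within-person dipping correlation 0.5, mean window cuts of 0.5–1.0 h (SD 0.5–1.0), and an ABP night varying by 0.75 h (SD) around the weekly mean. Let f be the fraction of the way from sleep to day SBP at which awake-in-bed SBP lies.

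| f | Spurious r | Two-sided false-positive rate |
|---|---|---|
| 0 | −0.05 to −0.09 | 11–19%, almost all negative |
| 0.25 | about 0 | 5–6% |
| 0.5 | 0.05–0.08 | 11–17% |
| 0.75 | 0.10–0.15 | 25–49% |
| 1 | 0.14–0.23 | 47–84% |

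With the ABP-night window lengths as covariates the rate was 4.4–7.6%. With a window fixed in advance it was 4.5–6.1%, as expected, since that removes the artefact by construction. These rates show sensitivity to the assumptions; they are not estimates for this trial.

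**The case against.** Several points against the concern stand and limit it.

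- **Timing.** A reader might infer that the artefact peaks at the post-CBT-I visit because it follows sleep restriction. The documents do not support that: restriction starts at Session 2 and the window is then widened, so the net shortening at that visit is unstated.
- **Direction.** A reader might infer that relabelling always deepens the dip. It does so only if awake-in-bed SBP is nearer waking than sleep level (less than about 8% below waking in the example). No document gives that BP.
- **Size.** A reader might set a within-person shift beside the 2.2 points and conclude that relabelling can supply all of it. That compares unlike quantities, because a shift common to all participants drops out of the regression.
- **Dilution.** Sleep efficiency averages several nights with event-marker confirmation; dipping uses one record. The link is weaker than a single shared window would give. The simulation allows for this.
- **Definition.** C.5 does not say whether the night runs from lights out to out of bed or from sleep onset to waking. The second reading would shrink the artefact.
- **Sleep does change.** Less wake in bed at constant sleep time is consolidated sleep, which the intervention intends. Only total sleep time is unchanged in the example.
- **Existing safeguards.** The 24-hour mean does not depend on the window, and D.2 adds other actigraphy measures, ISI and PSQI. They help interpretation but do not free dipping from the window. Nighttime mean BP uses the same split, and true dipping can change while the 24-hour mean stays flat.

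**Conclusion.** The structural point holds: exposure and outcome share a log-defined window, the intervention acts on it, and the primary model ignores its change. Some of the Aim 1 association may be relabelling. Under the assumed values, the artefact between thirds runs from about −0.6 to +1.4 points against 2.2, and the range includes zero. The figures rest on assumed BP levels, sleep time and window cuts, and on a night equal to time in bed. The documents do not support the inference that a positive result would be wholly a labelling effect. They support only that the planned analysis cannot separate the two explanations. The primary definition can stay, but a check should be planned beside it.

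**What to change.** Keep the primary definition of dipping and make these additions to the analysis plan:

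1. State which log times bound the ABP night at each visit.
2. Pre-specify a companion sensitivity analysis that recomputes dipping and nighttime SBP from the stored time-stamped readings over a window held constant within participant, namely the overlap of the logged sleep periods across visits. Say whether the hours outside the overlap but inside a logged period count as day or are left out.
3. Add a supporting model with change in time in bed and change in total sleep time in place of change in sleep efficiency, or add change in ABP-night window length as a covariate.
4. Report these beside the primary result, and read a positive association as evidence for the mechanism in light of whether it persists. This guides interpretation; it is not a pass/fail gate.

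The cost is plan wording and re-processing, with no new measurement. The overlap window has fewer night readings and loses some precision: at one reading per 30 minutes, about 14 in 7.0 h instead of 17 in 8.5 h. A fixed clock window is a poorer substitute, because it can count out-of-bed time as night and bias against a real effect.

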#### Echocardiogram

Patients with insomnia are at increased risk of heart failure and of cardiovascular events. A focused echocardiogram (2-D images of the heart in the parasternal long axis and apical 4-chamber views, pulsed wave Doppler of mitral inflow, and tissue Doppler imaging of the mitral annulus) will be performed to examine echocardiographic predictors of cardiovascular morbidity and mortality. Left ventricular mass, left ventricular global longitudinal strain (an index of systolic function), and measures of diastolic function of the left ventricle will be examined to determine if these parameters are modified by improved sleep quality. This will be performed pre-CBTI and at the 6 month follow-up. [name] will read all the echocardiograms and will be sent these images using DukeBox. The images will only include the date, therefore a transfer of a limited dataset of PHI has been established.

24-hour Urinary Catecholamines and Electrolytes. Patients will be asked to collect urine over a 24-hour period. Urine samples will be kept cold by storage in a portable cooler throughout each 24-hour sample period. Urine will be collected in two containers provided to each participant in a portable cooler, with careful instructions to collect daytime/awake urine in containers labeled accordingly, including the last collection before bedtime; any nighttime/sleep period urine collection will be collected in the container labelled “nighttime”, and participants will be instructed to void using that collection container as soon as they get up in the morning. Samples will be assayed for norepinephrine, epinephrine, and creatinine. Catecholamine levels will be expressed as urine concentration (g/ml) per urine concentration of creatinine (mg/ml), yielding norepinephrine and epinephrine values of g per mg creatinine for each sample. This provides catecholamine excretion indices that are corrected for individual differences in body size and urine volume. We will also assay for sodium and potassium as dietary habit changes may be contributory mechanisms of BP change, worthy of exploration. In prior studies of circadian changes in sympathetic activity, urinary catecholamine data have proven informative, with low subject burden and excellent compliance. The 24-hour urine collection will be done twice, before and after CBT-I.

Vascular Endothelial Function - Flow Mediated Dilation (FMD). Our approach for assessing endothelial function conforms to the recently published guidelines for assessment of flow-mediated arterial vasodilatation.

Longitudinal B-mode ultrasound images of the brachial artery, 4-6 cm proximal to the antecubital crease, will be obtained at end-diastole (ECG R-wave gated digital image capture) using a dedicated Acuson Sequoia ultrasound platform. All images will be acquired with participants supine, utilizing an 11 MHz linear array probe with stereotactic holder in our temperature-controlled clinical research

laboratory, by [name], RDMS, RVT, who has over 20 years of experience performing the standardized image acquisition protocols for our ultrasound FMD assessments. In an unpublished evaluation of 20 healthy men and women who underwent our FMD assessment protocol on two consecutive days, repeat FMD values showed a correlation of  $r=0.81$ ,  $p<.001$ , and a mean absolute difference of 0.64%. Images will be obtained and stored digitally at resting baseline, as well as during and following inflation to 220 mm Hg of an occlusion cuff placed around the forearm, 2 cm below the elbow. All arterial diameter measurements will be performed by the same experienced member of the research team, blinded to participant identity and the study phase at which the assessment was made, using edge detection software (Brachial Analyzer, MIA-LLC, Coralville, IA). FMD response will be assessed from 10-120 seconds post-deflation of the forearm cuff, with peak arterial diameter quantified using polynomial curve fitting, and FMD thereby defined as the maximum percent change in arterial diameter relative to pre-inflation resting baseline. As others have reported, using this rigorous standardization of FMD methodology, our FMD assessments will be obtained with optimal reproducibility, reflected in a coefficient of variation of approximately 10% or less. Peak hyperemic flow and shear stress will be derived by standard formulae based upon Doppler velocity measurements during the first 10 seconds following deflation of the occlusion cuff.

**Arterial Stiffness.** Aortic pulse wave velocity (PWV), measured using the Complior system (Artech Medical, Pantin, France), will be our validated index of central arterial stiffness. Pulse pressure waveforms will be recorded from the right carotid and right femoral arteries, and PWV through the descending aorta, measured in meter/sec, is calculated from measurements of pulse transit time and the distance travelled by the pulse, derived from the distance between the two recording sites. The PWV assessment will be performed by [name], RDMS, RVT, who has over 10 years of experience with this procedure. This will be performed pre-CBTI and at the 6 month follow-up.

**Blood Assays.** Blood will be drawn and processed by our research phlebotomist between 8:00 am and 10:00 am, after 12 hours of overnight fasting, on each of the four laboratory assessment visits, in order to measure: total cholesterol, HDL- and LDL-cholesterol, VLDL-cholesterol, and triglycerides; inflammatory activity measured by high sensitivity C-Reactive Protein (hsCRP); At baseline assessment only, thyroid stimulating hormone (TSH) will be assayed to ascertain if hypertension is due to hyper- or hypothyroidism.

**Atherosclerotic Cardiovascular Disease (ASCVD) Risk.** Although we are interested primarily in whether improved sleep quality will lower the mechanisms of insomnia-related CVD risk, we will also explore computed ASCVD risk (for participants aged  $\geq 40$  years) from the Pooled Cohort Equations recently validated and recommended by the clinical practice guideline expert panel of the American College of Cardiology/American Heart Association. These equations estimate the 10-year risk of a primary ASCVD event (including myocardial infarction and stroke) among patients without pre-existing CVD. Patients are considered to be at "elevated" risk if the Pooled Cohort Equations predicted risk is  $\geq 7.5\%$ . For example, a 50-year old white male smoker with a systolic BP of 130 mm Hg, no diabetes, and total cholesterol of 200 mg/dL with HDL cholesterol 30 mg/dL would have a 10-year ASCVD risk of 13.2%. Lowering systolic BP to 120 mm Hg and raising HDL to 50 mg/dL, with total cholesterol remaining at 200 mg/dL, would almost half his risk, reducing it to 6.9%. Indeed, we also have recently shown that both pharmacological and behavioral interventions to treat depression can lower the calculated 10-year risk of an ASCVD

event. Because several large population studies have shown that insomnia and short sleep duration are linked to hyperlipidemia, the CBT-I intervention holds promise for both lowering BP and improving lipid profiles, thereby reducing 10-year ASCVD risk.

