##### b. Protections Against Risk

As noted earlier, the primary risks for participants are those associated with confidentiality. To ensure that confidentiality is maintained, we will store our non-electronic patient records in locked cabinets within a locked area, with access limited to study staff. Electronic records will be maintained in a secure network setting, with access available only to selected study personnel. In addition to network security, individual workstations for data entry and analysis will be accessible only by password. Also as noted earlier, all electronic records will be identified only by a study identification number.

All project staff will have fulfilled Duke University mandatory HIPAA training requirements. All aspects of the study protocol will meet HIPAA requirements specified by the Human Studies Committee and the Privacy Office at Duke University.

The protocol will be approved by the Duke University Medical Center IRB before it is implemented. All investigators have completed the required education and certification in the protection of human research subjects.

In the unlikely event of an adverse medical event during assessment or any other on-site phase of study participation, the patient's attending physician and/or the emergency services at DUMC will be contacted immediately. In addition, the principal investigators and medical director of the study will be notified of all such events.

**Potential Benefits:** This study has several potential benefits. First, patients receiving CBT-I are likely to benefit from marked reductions in their insomnia symptoms and improvement in their sleep quality;

these benefits have been documented to persist for many years after completion of the 6-week CBT-I intervention. Study participants will also receive state-of-the-art evaluation of their blood pressure observed over 24-hours on four occasions, thereby providing themselves and their primary care physicians the most appropriate and valuable information on which hypertension management can be based. Our comprehensive assessments of CVD risk mechanisms will also be made available to participants' physicians upon completion of the study, again helping optimize their medical management.

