## Safety Monitoring

Although blood pressure will be monitored by research staff during the study, blood pressure management will continue to be up to participants' health care providers (HCPs). Patients who exhibit screening "office" averaged BP greater than 160/100 mm Hg across the two screening sessions will not be eligible to participate in the study and will be provided their screening BPs with the recommendation that they provide this information to their HCP within 72 hours. For participants already enrolled in the study, if "office" averaged BP values exceed 160/100 mm Hg, the participant will be provided those BP readings at that time, and will be encouraged to share the results with their HCP within 72 hours; with patient written consent, we also will provide the BP readings to their HCP. All eligible participants will have completed the CBT-I intervention within approximately 3 months from study enrollment. Both pre- and post-treatment ambulatory blood pressure records and study-assessed "office" blood pressures will be provided to participants at that time (i.e., after ~12 weeks), and with their consent (using a Redcap electronic medical authorization or paper authorization form), also will be provided to their HCP for follow-up as needed. In the event that participants do not have a HCP, a list of local family HCPs who are accepting new patients will be provided to them.

Participants will undergo follow-up assessments 6 months after the CBT-I intervention. Any intervening treatments including antihypertensive medications, will be documented. It should be emphasized that participants will not be prohibited from initiating pharmacologic treatment for high blood pressure at any time during the study. At all assessment phases, participants' medications will be documented. Upon completion of their participation in the study (approximately 9 months after initial screening assessments confirmed their eligibility), for participants who exhibit no improvement in their insomnia symptoms, we will refer them back to their HCP for consideration of alternative approaches to treating their insomnia.

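### Echo images reach the single reader with their acquisition date still on them, so the phase blinding promised for assessors in section C.5 is not protected for echocardiography

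*Combined protocol and SAP*

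**What the plan says.** The opening of section C.5 (Assessment of Mechanisms of Cardiovascular Risk) makes a general promise with no exceptions: "Assessors will be blinded to the study phase at which data are collected". The echocardiogram is described within that section.

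The Echocardiogram paragraph sets two time points: "This will be performed pre-CBTI and at the 6 month follow-up". One reader "will read all the echocardiograms and will be sent these images using DukeBox". On what the images carry, it says: "The images will only include the date, therefore a transfer of a limited dataset of PHI has been established". Left ventricular mass, longitudinal strain and diastolic measures "will be examined to determine if these parameters are modified by improved sleep quality".

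The flow-mediated dilation (FMD) paragraph in the same section is more specific. Its reader is "blinded to participant identity and the study phase at which the assessment was made". The echo paragraph has no equivalent sentence.

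**The concern.** The plan states a blinding property for all C.5 assessors and then describes an echo transfer that leaves the most obvious clue to phase on the images. With only two scans per participant, date order is phase order. Nothing in the documents says that the date is removed or shifted, that scans are recoded, or that they are read in random order.

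Left ventricular mass, strain and diastolic indices depend on tracing and judgement, so a reader who knows or suspects the phase can shift the readings without intending to. The trial has no comparison arm. It relies on the run-in as a within-participant control (section D.2), but echo is not repeated across the run-in. There is thus no untreated interval in which reader drift or expectation could be seen. At stake is the credibility of any statement about how echo measures changed from before CBT-I to follow-up.

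**Working it through.** The plan gives no figure for this point, so there is none to reproduce. The check asks how much a date reveals, and what that could do to the analysis.

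**Inputs**
- Two echo time points (Echocardiogram paragraph).
- Follow-up timing: "Participants will undergo follow-up assessments 6 months after the CBT-I intervention" (Safety Monitoring). CBT-I itself lasts 6 weeks (Design & Procedures).
- Linkage of a participant's scans: not stated for echo. The general rule is that "all electronic records will be identified only by a study identification number" (Protections Against Risk).
- Enrolment duration T: not given. Assumed to be 12 to 60 months.
- Sample: 150 with 15% attrition (Power and Sample Size Considerations), 150 × 0.85 = 127.5, taken as 128.

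**Gap between the two scans.** 6 months + 6 weeks ÷ (52/12 weeks per month) = 6 + 1.38 = 7.38 months, about 7.4.

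**Scans that can be linked.** The earlier date is always the pre-CBT-I scan. Phase is known for 100% of complete pairs.

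**Scans that cannot be linked.** Assume uniform enrolment over T months, complete follow-up, and a reader who knows roughly when the trial began and stopped enrolling. Scans from the first 7.4 months are all pre-treatment, and scans from the last 7.4 months are all follow-up. Together they make up a share gap/T of all scans. In between the two phases overlap evenly and a guess is right half the time. So accuracy = 0.5 + 0.5 × min(1, gap/T).

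| Assumed T (months) | gap/T | Best-guess accuracy |
|---|---|---|
| 12 | 0.615 | 81% |
| 24 | 0.308 | 65% |
| 36 | 0.205 | 60% |
| 48 | 0.154 | 58% |
| 60 | 0.123 | 56% |

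**Effect on the analysis.** The Aim 2 plan for risk mechanisms regresses the outcome on improvement in sleep efficiency. If the reader adds a constant c to every follow-up reading, c goes into the intercept and the slope does not move. A simulation agrees (4,000 runs, n = 128, no true effect, assumed c = 0.3 SD of the change). The mean slope was -0.0004 both with and without the shift. A test of the mean pre-to-follow-up change behaved differently: its false-positive rate rose from about 5% to about 92%. The 0.3 SD is illustrative. The documents give no basis for the size of any real reading bias.

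**The case against.** The date sentence is a privacy statement. It explains why a limited dataset is transferred. It does not say that the reader is told the phase, sees a visit label, or reads a participant's two scans together. Read literally, the images carry only the date and so have no identifier to pair on. A reader might infer that the phase blinding is simply not delivered, or that the two paragraphs contradict each other. The documents do not support either. A date is not a phase label, certainty needs linkage that is not stated for echo, and the echo paragraph is silent on how blinding is kept rather than opposed to it. That objection stands. What remains is that no safeguard is written down, that the study-ID rule makes linkage plausible, and that even unlinked dates leak some information.

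A reader might also infer that, without a control arm, reader expectation feeds straight into the trial's conclusions with nothing to cancel it. That is not supported either. The stated question is whether echo measures change with improved sleep quality, and section D.2 says the aim is not to test the efficacy of CBT-I. The contrast between participants with larger and smaller sleep changes removes a shift common to all follow-up scans. To bias the slope, reading error would have to track each participant's sleep-efficiency change, and nothing in the documents gives the reader that information. The mean-change test behind the 92% figure is not specified for echo anywhere.

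Finally, echo is not among the four components of Hypothesis 2, is absent from the power section, and is not the primary outcome, which is nighttime blood pressure dipping. This also stands and limits the weight of the point.

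**Conclusion.** The point holds in a limited form: the plan promises phase blinding that its written echo procedure does not protect. The leak is complete for any scans the reader can link. For unlinked scans it is partial, with best-guess accuracy from 81% down to 56% over assumed enrolment of 12 to 60 months, concentrated early and late in the trial.

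The primary result is not threatened. On the assumption that echo measures are analysed with the Aim 2 model for mechanisms, which does not name them, a uniform reading shift leaves the planned slope unbiased. The exposure lies in any report of mean echo change from before CBT-I to follow-up. Its size cannot be derived from the documents.

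**What to change.** Before transfer, remove or mask the acquisition date on the image and in the file header, and give each scan a random code unrelated to participant or visit. Release pre-treatment and 6-month scans in mixed batches in random order, and have someone other than the reader hold the key. Add a sentence to the Echocardiogram paragraph saying so, parallel to the one for FMD. If masking is already done in practice, that sentence alone settles the matter. If scans have already been read with dates visible, only a blinded re-reading of the stored images would restore the property.

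The cost is a de-identification step and a code list, with no added visit, reader or procedure. The downside is delay: the first mixed batch cannot be released until follow-up scans exist, about 7.4 months after the first pre-treatment scan. Later batches need to close in time for results to reach participants' physicians at study completion, as the Potential Benefits text promises. A side gain is privacy: the paragraph gives the date as its reason for a limited-dataset transfer, and masking removes that reason.
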